1. RATIONALE OF THE STUDY

Bladder problems and urinary diseases, also known as Lower Urinary Tract Symptoms (LUTS), are common worldwide (Todhunter-Brown et al., 2022). One of these problems is Urinary Incontinence (UI), defined as “the complaint of any involuntary leakage of urine” (Abrams et al., 2003; Hylen et al., 2010). UI can be classified into three main subtypes. Stress UI (SUI) is the urine loss provoked by exertion, physical effort, sneezing or coughing; Urge UI (UUI) refers to urine leakage accompanied by a sense of urgency that is defined as a sudden and compelling desire to void urine (Haylen et al., 2010; Bo et al., 2017); Mixed UI consists of the combination of SUI and UUI (Abrams et al., 2003).

UI has been identified as a World Health Organization health priority (Parpio, Minaz & Haider, 2022), also because individuals with UI are projected to increase with time, with the greatest increase in burden anticipated in developing regions (Irwin et al., 2011). A worldwide prevalence study conducted in the last decade reported that an estimated 21.5% of the 2008 worldwide population ≥ 20 years (approximately 348 million subjects out of 4.3 billion) was affected by UI (Irwin et al., 2011). Particularly, SUI is the most common UI type (5.9% in women vs 0.49% in men in 2008). Numbers of patients affected by UUI in 2008 were 49 million, while 54 million individuals were affected by MUI (Irwin et al., 2011).

Currently, the Italian epidemiology for UI is approximately 5 million people (the 8.7% of the population), of which 3 million are women (Fincopp, 2022). According to the Italian Institute for Statistics (ISTAT), the Italian population is aging, and the average age of the population ranges between 40 and 65 years old (Sistema Statistico Italiano and Istituto Nazionale di Statistica (ISTAT), 2021). Statistics suggest focusing on this specific range of age, in which population's high quality of life and healthy lifestyle is expected, also because they are socially active subjects. In addition, the range 40-65 represents the starting point of significant occurrence of UI in the female population (Irwin et al., 2006; Wieland et al., 2019; Fincopp, 2022). In fact, a study conducted in an Italian urban area (Siracusano et al., 2003), investigating the UI prevalence by age subgroups in a sample of 2900 women, showed that more than one in four women suffered from incontinence episodes from 40 years of age onwards. Another Italian prevalence study (Bortolotti et al., 2000) interviewed 2767 women ≥ 40 years old and 2721 men ≥ 50 years old to assess the frequency of UI, finding that 3% of male sample and 11% of female participants reported at least one episode of UI during the previous year. Female data were substantially confirmed by an Italian cross-sectional study carried out in 2002 (Parazzini, Lavezzari & Arbitani, 2002). A total of 13365 women (mean age, 60.3 years) were identified by 774 general practitioners: the frequencies of UI were 10.2%. Instead, for men older than 40 years (mean 64.8 years) a fairly higher percentage than in previous data (8.3% vs 3%) experienced UI (Parazzini, Lavezzari & Arbitani, 2002). This discrepancy is probably linked to the fact that, in the study by Bortolotti and colleagues, men between the ages of 40 and 50 were not enrolled (Miano et al., 2012).

Regarding gender difference, UI affects both women (Sussman et al, 2020) and men (Gacci et al., 2022), but it is more common in female than in male population (Markland et al., 2011; Milsom & Gyhagen, 2019; Monticone et al., 2020) and women are more severely affected than men (Aslan et al., 2008), due to obstetric, gynecological and hormonal causes (Sensoy et al., 2013): these data highlight the importance of the phenomenon and the need to study in depth the female UI condition.

In addition, UI negatively influences the physical, psychological, social and financial life of the affected people (Batmani et al., 2021; Parpio, Minaz & Haider, 2022). The health-related quality of life impact

 
I.R.C.C.S. Ospedale San Raffaele
	
STUDY PROTOCOL
	
WUIPS Version n. 1 23.08.2023

---	------------------------------	---

of incontinence is similar to that observed with other chronic medical conditions like osteoarthritis, chronic obstructive pulmonary disease, and stroke (Subak et al., 2006). Specifically, it was seen that UUI is the UI subtype with the higher impact on the quality of life (Aslan et al., 2009), due to the frequency of incontinence episodes and the urge to urinate, which interrupts the daily routine. Reducing these symptoms is a priority for women and it is demonstrated by their willingness to pay for continence improvement (Subak et al., 2006). In fact, women with UI consume significantly higher medical resources and incur higher costs to payers, compared to women without this problem (Datar et al., 2022).

Although it is a widely discussed literature topic, UI is an underestimated condition (Tran & Puckett, 2022). In fact, sometimes people do not report this problem, because it is still considered a taboo and a source of shame and embarrassment (Elenskaia et al., 2011). In addition, the last published Italian prevalence studies date back to the first decade of the new millennium (Bortolotti et al., 2000; Parazzini, Lavezzari & Arbitani, 2002; Siracusano et al., 2003). For this reason, a prevalence study focused on UI in Italy could provide significant information.

The current study will indagate the prevalence, predictors and effects (quality of life and costs) of UI in middle-aged women (40-65 years old) identified in four hospitals in Northern Italy, which are the reference centers for Vita-Salute San Raffaele University (UniSR).

2. STUDY DESIGN

A multicenter prospective and prevalence observational study will be conducted. A prevalence study is essential for establishing the distribution of the condition in the population and projecting the need for health and medical services supporting health care professionals to make preventive and treatment decisions. The study will follow the STrengthening the Reporting of OBservational studies in Epidemiology (STROBE) Checklist (Vandenbroucke et al., 2007).

3. OBJECTIVE

The study will aim to punctually investigate and describe prevalence, predictors, quality of life and costs of Urinary Incontinence among female patients, female caregivers and female personnel in four hospitals in Northern Italy.

4. OUTCOMES

Primary outcome

- Prevalence of middle-aged women with urinary incontinence.

Secondary outcomes

- Description of UI and related predictors, quality of life, social impact and costs.
- Association between UI and related predictors, quality of life, social impact and costs.

5. EXPECTED RESULTS

The collection of data and information through this study will aim to:

- a) Understand the percentage of middle-aged women with UI.

 
I.R.C.C.S. Ospedale San Raffaele
	
STUDY PROTOCOL
	
WUIPS Version n. 1 23.08.2023

---	------------------------------	---

- b) Describe the socio-demographic and clinical characteristics of women with UI.
- c) Identify UI predictors.
- d) Describe the quality of life, social impact and costs of women with UI.

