8. PARTICIPANT REGISTRATION

Data collection will be carried out through the use of two questionnaires validated in Italian language and a survey built by the researchers on the basis of the scientific literature.

Two different paths have been designed to recruit participants, depending on whether they are female personnel or female patients and female caregivers:

 
I.R.C.C.S. Ospedale San Raffaele
	
STUDY PROTOCOL
	
WUIPS Version n. 1 23.08.2023

---	------------------------------	---

- for healthcare professionals and administrative workers of the four hospitals, one week before the administration of the data collection tools (a survey and two validated questionnaires), an email will be sent to the work account to present the topic and the aim of the study. A second email will then be sent with a link to access the online survey/questionnaires (RedCap) and with a deadline by which to fill it out. The email will be sent to all workers, asking for the compilation only to women of 40-65 age range group and who meet the inclusion criteria. Participants will agree to a brief privacy policy and electronic release of informed consent before completing the survey and the questionnaires.
- for female patients and female caregivers' registration, participants will be recruited at the central admission and at the private admission of four hospitals in Northern Italy. At recruitment, inclusion and exclusion criteria will be evaluated through a brief preliminary interview, lasting about a couple of minutes. It will take place immediately before the administration of the questionnaires at the central and private reception of the hospitals involved. On this occasion, a researcher in charge of data collection will ask the participant for information on: age, pregnancy/puerperium status and past history of gynecological surgery. Each participant who joins the study will be provided with a paper module, containing the survey and the questionnaires, marked with a progressive identification number: after signing the informed consent, all participants will be asked to answer questions voluntary and anonymously at the moment and return the completed module to researchers.

Data will be collected anonymously by a paper module for patients and caregivers and by RedCap for healthcare professionals and administrative workers. Then, the data on the platform will be extracted to the eCRF; the paper data will be uploaded to the eCRF by the researchers.

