UI prevalence and symptomatology	Lifestyle factors	
 Unhealthy voiding behavior (Hu and Pierre, 2019) and low physical activity may contribute to UUI onset (Li et al., 2023) Smoking cessation is a general public health measure and has been shown to be weakly associated with improving urgency, frequency and UI (Danforth et al., 2006; Harding et al., 2023) Decrease in fluid intake may improve some symptoms in patients with SUI and idiopathic detrusor overactivity (Swithinbank et al., 2005) Reduction of caffeine intake may reduce symptoms of frequency and urgency (Harding et al., 2023) An association was seen between alcohol consumption and urinary incontinence in middle-aged and older women (Lee & Hirayama, 2012)
	Frequency of urine leakage	To assess the severity of UI among female, we need measuring the “frequency” and “usual amount” of leakage ranged from “moderate” to “strong” (Avery et al., 2004)
	Perceived quantity of urine leakage	
	Type of urine leakage	It is focused on subtypes of urinary incontinence (SUI, UUI and MUI) (Abrams et al., 2003)
	Time of onset of urine leakage	The mean age in which urine leakage begins seems to be lower for SUI compared to MUI and UUI (Thangarajah et al., 2020)

 
I.R.C.C.S. Ospedale San Raffaele
	
STUDY PROTOCOL
	
WUIPS Version n. 1 23.08.2023

---	------------------------------	---

UI quality of life, social impact	General interference with daily life	The measurement of UI should incorporate the impact that the condition may have on quality of life (Avery et al., 2004)
	Interference with specifical activities	
Specifically:
 
 • Physical Activity • Social Relationships • Travel • Emotional Health 
(Monticone et al., 2021; Shumaker et al., 1994)

	Interference with sexual life	Some articles report that UI affects sexual aspects of the individual (Felsted & Supiano, 2019; Marques et al., 2015). According to other studies, sexual activity does not seem to be damaged by UI (Siracusano et al., 2003)
Costs	Work productivity	UI imposes a high economic burden because of work productivity loss (Goren et al., 2014)
	Weekly costs of hygiene care products	UI is associated with substantial routine care “costs” (Subak et al., 2006)

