16. Quanti parto cesarei ha avuto?

- 0
- 1
- 2

□ > 3

17. Pratica attività fisica in maniera frequente?

18. Fuma o ha mai fumato?

1. Attuale fumatore 2. Ex fumatore 3. Mai fumatore

19. Se fuma o fumava, quante sigarette al giorno consuma/consumava?

1-5 > 10-20
 > 5-10 > 20

20. Quanti caffè assume in media al giorno?

0 2
 1 3

21. Quanti drinks alcolici assume in media a settimana?

 0	 15-21
 1-7	 ≥ 22
 8-14	

22. Quanta acqua beve in media al giorno?

- 1. Meno di $\frac{1}{2}$ litro
- 2. Tra $\frac{1}{2}$ litro e un litro
- 3. Più di un litro, fino a un litro e $\frac{1}{2}$
- 4. Più di un litro e $\frac{1}{2}$

23. Quante volte al giorno svuota la vescica mediamente?

- 1. Ogni ora o più frequentemente
- 2. Ogni due-tre ore circa
- 3. Ogni quattro ore o meno frequentemente

ICIQ-UI Short Form (Italian)

A molte persone capita, a volte, di avere delle perdite di urina. Stiamo tentando di determinare quante persone abbiano delle perdite di urina e quanto ciò costituisca, per loro, un problema. Le saremmo grati se rispondesse alle seguenti domande facendo riferimento a come si è sentita, in media, nelle ULTIME QUATTRO SETTIMANE.

24. Con quale frequenza le capita di avere delle perdite di urina? (faccia una crocetta su una sola casella)

- 1. Mai
- 2. Una volta la settimana o meno
- 3. Due tre volte la settimana

- 4. Circa una volta al giorno
- 5. Più volte al giorno
- 6. Continuamente

25. Ci piacerebbe sapere qual è, secondo lei, la quantità di urina che perde. Quanta urina le capita di perdere di solito (sia quando indossa una protezione che quando non la indossa)? (faccia una crocetta su una sola casella)

- 1. Per niente
- 2. Una piccola quantità
- 3. Una discreta quantità
- 4. Una notevole quantità

26. In generale, in che misura le perdite di urina hanno interferito con la sua vita quotidiana? La preghiamo di fare un cerchietto attorno ad un numero tra 0 (per niente) e 10 (moltissimo)

0 1 2 3 4 5 6 7 8 9 10

per niente

moltissimo

27. In che occasione le capita di avere delle perdite di urina? (Indichi, tra le seguenti, tutte le situazioni che corrispondono al suo caso)

- 1. Mai – non ho perdite di urina
- 2. Ho perdite di urina prima di riuscire a raggiungere il bagno
- 3. Ho perdite di urina in occasione di colpi di tosse o starnuti
- 4. Ho perdite di urina quando sono addormentata

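### One anonymous form per woman cannot identify predictors of urinary incontinence among factors that leakage itself can change

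*Protocol*

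**What the plan says.** Section 2 states: "A multicenter prospective and prevalence observational study will be conducted". Section 1 announces that the study will examine "prevalence, predictors and effects (quality of life and costs) of UI in middle-aged women". Section 3 repeats predictors as part of the aim, and Section 5(c) lists "Identify UI predictors" as an expected result. The introduction to the survey (Appendix) tells respondents that it concerns factors that may predispose to the onset of incontinence.

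Section 4 is more cautious. The secondary outcome there is "Association between UI and related predictors, quality of life, social impact and costs".

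Section 8 describes a single completion. Patients and caregivers are to "answer questions voluntary and anonymously at the moment and return the completed module to researchers". Personnel receive one link to an online form with a deadline. Section 16 says that the data are anonymous and cannot be traced to an individual. No second assessment is described anywhere.

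Section 9.1.1 assigns questions 1–23 to the predictors of incontinence. Table 1 (Section 9) supports the lifestyle items with statements such as "Decrease in fluid intake may improve some symptoms in patients with SUI and idiopathic detrusor overactivity". The matching survey item, question 22, is "Quanta acqua beve in media al giorno": average daily water intake, in the present tense.

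**The concern.** A predictor of onset has to come before onset. Here exposure and outcome are read from the same form on the same occasion, and several of the exposures are things a woman may change because she leaks. For these, an association may run from leakage to behaviour rather than the other way. The study could then report a consequence of incontinence as its predictor. Low water intake could look harmful because women with leakage have cut down. Coffee could look protective because they have stopped drinking it.

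What is at stake is expected result (c) and how the secondary associations are read. A reader who meets prospective in the design section and predictors in the results will assume a time order that the data do not contain.

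**Working it through.** The protocol gives no sample size, effect size or model for this question, so there is no figure to reproduce. The check is mainly a comparison of sections, followed by a small illustration.

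**Step 1: number of assessments and time windows.** There is one form per woman, anonymous, with no follow-up (Sections 8 and 16). The ICIQ UI-SF covers the preceding four weeks (Section 9.1.2). Questions 17 and 20–23 ask about present habits without a date. Question 8 asks whether the woman has or has ever had each condition, again without a date. Exposure and outcome windows therefore overlap or cannot be ordered.

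**Step 2: what is classed as a predictor.** The row structure of Table 1 is hard to read in the extracted text, but Section 9.1.1 settles it: questions 1–23 all count as predictors, including 8, 17 and 20–23.

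**Step 3: where the protocol itself shows the opposite direction.**

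| Variable | Treated as predictor | Sign that leakage may change it |
|---|---|---|
| Physical activity | Table 1 (contributes to onset of urge incontinence); question 17 | Question 29 asks whether leakage has affected physical recreation |
| Depression | Table 1; question 8 | Question 33 asks whether leakage has affected emotional health, naming depression |
| Fluid intake | Table 1; question 22 | Table 1 says that less fluid may ease symptoms, a reason to cut down |
| Caffeine | Table 1; question 20 | Table 1 says that less caffeine may ease frequency and urgency, likewise a reason to cut down |
| Voiding frequency | Question 23 | Close to a urinary symptom in its own right |

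Alcohol (question 21) and sleep disturbance (question 8) are also undated, and leakage could plausibly change them.

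**Step 4: can the order be recovered from other items?** Only question 35 dates leakage, in four duration bands and for symptomatic women only. Question 14 (birth year of the last child) can be compared with it roughly. Question 11 records current menopausal status without an age or date, so question 35 cannot show whether menopause came before or after onset. Question 18 separates current from former smokers but gives no date of stopping.

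**Step 5: is the limitation acknowledged?** Section 12.1 names recall bias and underreporting bias. It does not name reverse causation.

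**Step 6: illustration of size.** Assume that the exposure has no causal effect on incontinence. Let e be its prevalence in women without incontinence, and s the share of affected women who changed the behaviour after onset. The values of e and s are assumptions; the protocol gives neither.

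For low water intake, s is the share cutting down among affected women who would otherwise drink more. The prevalence in affected women is e1 = e + (1 − e)s, and OR = [e1/(1 − e1)] / [e/(1 − e)]. With e = 0.40, the reference odds are 0.40/0.60 = 0.667.

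| s | e1 | Odds | OR |
|---|---|---|---|
| 0.10 | 0.40 + 0.60 × 0.10 = 0.46 | 0.46/0.54 = 0.852 | 1.28 |
| 0.20 | 0.40 + 0.60 × 0.20 = 0.52 | 0.52/0.48 = 1.083 | 1.62 |
| 0.30 | 0.40 + 0.60 × 0.30 = 0.58 | 0.58/0.42 = 1.381 | 2.07 |

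For giving up coffee, e1 = e(1 − s). With s = 0.20:
- e = 0.40 gives e1 = 0.32 and OR = (0.32/0.68)/(0.40/0.60) = 0.71.
- e = 0.60 gives e1 = 0.48 and OR = (0.48/0.52)/(0.60/0.40) = 0.62.

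Coffee would look protective although it has no effect.

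**The case against.** The strongest reply is that the formal secondary outcome in Section 4 already speaks of association, that Section 3 aims to investigate and describe, and that prospective beside prevalence may mean only that the data are newly collected. No follow-up analysis is promised, and the choice of covariates may be left to an analysis plan that is not shown.

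Part of this stands. Section 4 makes the repair mainly one of wording. But Section 4 still calls the factors predictors and does not cancel Section 5(c) or the onset language in the survey introduction. The protocol does not define prospective in the weaker sense. No analysis plan can supply a time order that was not collected.

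A reader might also infer three stronger things that the protocol does not support:
- *That the quality-of-life and cost results fail for the same reason.* The word effects appears in Section 1 with that meaning. Questions 28–34, 36 and 37 ask what leakage has affected, and questions 38–40 ask about spending, visits and treatment for leakage. The direction is built into the question, so the impact wording can stay.
- *That the coefficients for age or parity will be distorted.* This would follow only if the leakage-modifiable items entered the same model. Section 13 names no such model.
- *That the odds ratios above measure the bias.* They follow from assumed shares.

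**Conclusion.** The point holds for variables that leakage can change: activity, coffee, alcohol, water, voiding frequency, sleep disturbance and depression. For these the protocol claims a property that a single anonymous questionnaire does not have, and its own form treats activity and depression as both predictor and consequence. It does not extend to age, nationality, education, parity or mode of delivery, which leakage does not alter.

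The size is not known. The odds ratios of 1.28 to 2.07 assume a 40% baseline and 10% to 30% switching. They show that modest behaviour change could create an apparent predictor, not that it has done so. The conclusion about wording and design does not depend on them.

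The matter concerns a secondary result. The primary outcome, prevalence, is unaffected.

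**What to change.** 1. Section 2: call the study cross-sectional. If prospective is kept to mean newly collected data, say so.
2. Sections 1, 3 and 5(c): replace predictors with associated factors, in line with the association wording of Section 4, and align the survey introduction. Keep the impact wording for quality of life and costs.
3. Report current behaviours, voiding frequency, sleep disturbance and depression as correlates in a separate table. Keep them out of any model used to estimate associations for factors that leakage does not change: age, nationality (question 2 does not collect ethnicity), education, parity and mode of delivery.
4. Assign the remaining Table 1 variables explicitly: BMI, smoking, menopause, surgery and the other comorbidities. Treat those whose order relative to onset is unknown as correlates. Question 35 should not be used to date menopause, because question 11 carries no date.
5. Section 12.1: add reverse causation to the named biases.

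The cost is a protocol amendment (shared with the Ethics Committee, as Section 14 provides), an edit to the survey introduction and one extra table. No new data are needed. The downside is a more modest claim for a secondary result.

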6. STUDY POPULATION

All female patients, female caregivers, female healthcare professionals and female administrative workers who meet the inclusion criteria will be included. Participants will be enrolled in four centers in Northern Italy which are the reference centers for UniSR: San Raffaele hospital in Milan, San Raffaele Turro hospital in Milan, Zingonia Policlinico San Marco (BG) and Policlinico San Pietro in Ponte San Pietro (BG).

7. INCLUSION/EXCLUSION CRITERIA

7.1 Inclusion criteria

- Female sex
- Middle age (40-65 years old)
- Informed consent signed
- Comprehension of written and spoken Italian language
- Female outpatients intended for any hospital unit (outpatient clinic, day surgery and day hospital patients included) and every female caregiver respecting the previous inclusion criteria, recruited at the central admission and at the private admission of the four hospitals involved
- Female workers (healthcare professionals and administrative personnel) of the four hospitals

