7.2 Exclusion criteria

- Male sex
- Young age (< 40 years) and older age (> 65 years)
- Pregnant women
- Puerperium women (up to 40 days post-partum)
- Women who had undergone urinary and gynecology surgery

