12.1 Bias risk

The included population could present Recall Bias (Delgado-Rodríguez, 2004) during the survey filling, particularly with the ICIQ-UI SF, because it refers to the last four weeks before the filling. This study could present the Underreporting Bias (Delgado-Rodríguez, 2004) because the survey asks for behaviors that negatively affect the personal and social life. The researchers decided to use a bias risk assessment tool during the drafting of the protocol to ensure the study quality. This tool will also accompany the writing of the paper in the future. It consists of a modification and an upgrade of the existing tool developed initially by Leboeuf-Yde and Lauritsen (Leboeuf-Yde & Lauritsen, 1995; Hoy et al., 2012). The tool is based on the Grades of Recommendation, Assessment, Development and Evaluation (GRADE) and Cochrane approaches (Higgins & Green, 2008; Terracciano et al, 2010).

The tool consists of 10 items addressing four domains of bias plus a summary risk of bias assessment: items 1 to 4 assess the external validity of the study (domains are selection and nonresponse bias), and items 5 to 10 assess the internal validity (items 5 to 9 assess the domain of measurement bias, and item 10 assesses bias related to the analysis) (Hoy et al., 2012). Table 3 illustrates the items of the risk of bias tool.

After completing the reporting of the manuscript (except for the risk of bias assessment), two blinded raters will give their opinion on the quality of the study. Response options for individual items (from 1 to 10) will be "low" or "high" risk of bias (if there will be insufficient information in the report to permit a judgment for a particular item, then the item will be deemed to be at high risk of bias). Response options for the summary assessment (item 11) will be "low", "moderate", or "high" risk of bias (Hoy et al., 2012). Overall interrater agreement will be calculated by considering each of the 10 items plus the summary assessment.

Table 3 - The items of the risk of bias tool

#	Item
1	Was the study's target population a close representation of the national population in relation to relevant variables?
2	Was the sampling frame a true or close representation of the target population?

 I.R.C.C.S. Ospedale San Raffaele	STUDY PROTOCOL	WUIPS Version n. 1 23.08.2023
--	-----------------------	--

3	Was some form of random selection used to select the sample, or was a census undertaken?

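### Women attending because of urine leakage enter the prevalence sample unflagged, because neither the desk interview nor the survey records the reason for the visit

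*Protocol*

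**What the plan says.** Section 7.1 of the protocol admits "Female outpatients intended for any hospital unit (outpatient clinic, day surgery and day hospital patients included", together with caregivers, recruited at the central and private admission desks. The closest exclusion, in section 7.2, is "Women who had undergone urinary and gynecology surgery". It looks only at past operations, so a first visit for leakage, or a first operation still to come, does not exclude a woman.

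Under section 8 the researcher at the desk "will ask the participant for information on: age, pregnancy/puerperium status and past history of gynecological surgery". The unit visited and the reason for the visit are not on that list, and none of the 40 questions in the Appendix asks for them. Question 39 asks whether specialist visits for leakage have taken place, which is a different matter. Nor does any question separate patients from caregivers, who complete the same paper module.

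The target is worded in two ways:
- Broad: the primary outcome in section 4 is "Prevalence of middle-aged women with urinary incontinence", section 5 aims to "Understand the percentage of middle-aged women with UI", and section 2 calls a prevalence study "essential for establishing the distribution of the condition in the population".
- Narrow: section 3 places the investigation "among female patients, female caregivers and female personnel in four hospitals in Northern Italy".

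Section 12.1 states that "The included population could present Recall Bias" and also expects underreporting. It does not mention selection by reason for attendance.

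**The concern.** Under the broad wording, the sample should not contain women because they leak. Attendance for leakage brings women with the outcome to the desk more often than women without it, so the patient group over-represents cases. Pooling three groups is a separate matter: reporting each group on its own leaves this distortion inside the patient group, and a larger sample does not shrink it.

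The secondary associations are exposed too. Several comorbidities listed as predictors in Table 1 can also bring a woman to hospital. Among attenders, the relation between those conditions and incontinence may therefore differ from that among women in general.

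A statistical analysis plan cannot repair this afterwards. The variable is not collected and the data are anonymous, so it cannot be recovered. Question 39 is a weak substitute: it misses women at their first visit and picks up earlier visits by women who are attending for something else today.

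**Working it through.** The protocol gives no precision or sample-size calculation, so there is no figure of its own to reproduce. What follows shows scale only.

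**Inputs**
- p0, prevalence without this selection: 25% and 45%, the range that section 11 attributes to most studies; 10.2%, the Italian figure there, as a low case.
- s, the share of patients attending because of leakage: not in the documents; assumed 2% and 5%.
- w, the patients' share of the whole sample: not in the documents; assumed one half, then one quarter and three quarters.
- n = 2,900: the larger of the two reference samples in section 11. It is not a planned size for this study.

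**Patient group.** If every woman attending for leakage reports it, observed prevalence = s + (1 − s)p0, so the rise = s(1 − p0).

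**Pooled figure.** Rise = w·s(1 − p0), because caregivers and personnel are not selected by a visit of their own.

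**Sampling error of the pooled figure.** 95% half-width = 1.96·√(p0(1 − p0)/n).

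| p0 | s | Rise among patients (points) | Pooled rise, w = 0.5 (points) | Half-width, n = 2,900 (points) |
|---|---|---|---|---|
| 10.2% | 2% | 1.80 | 0.90 | 1.10 |
| 10.2% | 5% | 4.49 | 2.25 | 1.10 |
| 25% | 2% | 1.50 | 0.75 | 1.58 |
| 25% | 5% | 3.75 | 1.88 | 1.58 |
| 45% | 2% | 1.10 | 0.55 | 1.81 |
| 45% | 5% | 2.75 | 1.38 | 1.81 |

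For example, at p0 = 25% and s = 5%: 0.05 × 0.75 = 3.75 points among patients, and 0.5 × 3.75 = 1.88 points pooled. With w = 0.25 or 0.75 the pooled rise there is 0.94 or 2.81 points.

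**Break-even.** The pooled rise equals the half-width when w·s = half-width/(1 − p0). That is 1.23%, 2.10% and 3.29% of the whole sample at p0 of 10.2%, 25% and 45%. With patients at one half, the corresponding s is twice as large: 2.5%, 4.2% and 6.6%.

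**Net direction.** Table 1 calls previous pelvic or uro-gynaecological surgery positively associated with stress incontinence, so excluding such women lowers prevalence. Suppose a fraction e is excluded and prevalence among them is r times that of the others; both values are assumed. With overall prevalence 25% and r = 1.5, prevalence among those left is 25%/(1 − e + 1.5e):
- e = 10%: 25/1.05 = 23.81%. Adding 0.5 × 0.05 × (1 − 0.2381) = 1.90 points gives 25.71%, a net +0.71.
- e = 20%: 25/1.10 = 22.73%. Adding 0.5 × 0.05 × (1 − 0.2273) = 1.93 points gives 24.66%, a net −0.34.

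The sign changes within a modest range of assumptions, before underreporting is counted.

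**The case against.** The strongest reply is that section 3 defines the target as the patients, caregivers and personnel of these four hospitals. On that reading a woman attending for leakage belongs in numerator and denominator alike, and removing her would bias the estimate downward. This stands for section 3, but sections 2, 4 and 5 use wider wording, and the protocol does not say which governs the primary figure. Even under section 3, a reader needs to know how many patients came because of leakage in order to interpret the result.

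A reader might infer that the primary prevalence is inflated overall. The documents do not support that: the surgery exclusion and the underreporting expected in section 12.1 both act downward.

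A reader might also infer that each such woman is certain to count as a case. The ICIQ UI-SF covers four weeks, participation is voluntary, and a woman under treatment may currently be dry. The formula is therefore an upper value for a given s.

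Nor can the bias be said to exceed sampling error in general. Compared like with like, pooled against pooled, it does so in some rows of the table and not in others. Setting the rise among patients against a whole-sample half-width would exaggerate it.

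Finally, the risk-of-bias tool in section 12.1 contains items on representativeness and selection. It rates the finished report and does not supply the missing variable.

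**Conclusion.** The concern holds in a limited form. Women attending because of leakage are eligible and cannot be identified in the data. On the population reading this is selection on the outcome within the patient group.

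Its upward contribution is s(1 − p0) among patients: 0.55–0.75 points for each percentage point of s at p0 of 25–45%, hence about 1.1–3.8 points for s of 2–5%. The pooled contribution is smaller in proportion to the patient share. These sizes rest on assumed values of s and w and on all such women reporting leakage.

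The documents establish neither the size nor the net direction of the bias in the primary figure. The case for acting is that this component is unmeasured and cannot be measured later, while measuring it at recruitment costs very little.

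**What to change.** Before recruitment:

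1. Add two items to the self-completed paper module: participant type (patient or caregiver) and, for patients, whether today's visit is for urine leakage. They should not go in the face-to-face interview. That interview precedes consent, section 1 describes the subject as a source of shame, and only the module is described as being entered in the eCRF.
2. Report prevalence by group (patients, caregivers, personnel). For patients and overall, give it both with and without women attending for leakage.
3. Repeat the predictor associations without these women as a sensitivity analysis. Do not drop women attending for prolapse, urinary infection or other pelvic-floor problems: prolapse and urinary infection are listed predictors, and removing them would select on exposure.
4. Name this selection in section 12.1, and state which target population the primary figure describes.

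The cost is one or two extra items and one additional analysis. The estimate without these women may be slightly lower and may itself slightly understate population prevalence, which is why both figures should be shown.
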